Interim analysis may be performed throughout the duration of the registry.

8.5. *Minimum and Maximum Patient Recruitment for Analysis*

Study enrollment will be competitive. There is no minimum or maximum number of patients that can be enrolled per site.

8.6 *12M Follow-Up Analysis and Minimization of Bias*

A minimum of 100 and up to a maximum of 120 subjects will be re-enrolled into the registry to complete the 12M follow-up visit. Bias will be minimized by contacting subjects who were treated within a specific timeframe designated by the Sponsor (for example, September 2018 to July 2019). Sites will be extended an invitation to participate in the study if they have enrolled at least 10 subjects within the identified timeframe in order to justify study costs incurred to keep the site open, submit amendments to the appropriate ethics committee, bandwidth of the site research team, etc.

The subset followed to one year is expected to be similar to the overall cohort in baseline patient characteristics. Baseline data for the 12M subset will be analyzed and compared to the overall cohort to demonstrate that the subset is representative of the overall cohort. If there are differences in the baseline characteristics of the subset and the overall cohort, these will be further evaluated and assessed as to their potential impact on the 12M results.

To test for generalizability of 12-month outcomes, patients undergoing 12-month follow-up will be compared to patients not undergoing 12-month follow-up in a pre-specified analysis of baseline demographics, clinical characteristics, procedural variables and in-hospital/30-day end-point outcomes.

Only AEs related to the MANTA access site or the ipsilateral leg will be collected at the 12M visit. AE data from the 12M visit will be analyzed separately from the primary safety endpoint, as 12M data will only be available on a subset of the study cohort and the primary safety endpoint is events through 30-days.

9. Adverse Events

9.1. *Definitions*

Refer to Section 4 for the definitions of the following terms associated with adverse events:

- Adverse Event
- Adverse Device Effect
- Device Deficiency
- Serious Adverse Event
- Serious Adverse Device Effect
- Unanticipated Serious Adverse Device Effect

9.2. *Potential Adverse Events and Adverse Device Effects*

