The primary responsibilities of the CEC over the course of the study are to review and refine serious adverse event definitions, and to review and adjudicate serious adverse events.

The CEC will determine if each reviewed adverse event meets the definition of a VARC-2 Major femoral vascular complication or a VARC-2 Minor femoral vascular complication or neither definition. For each AE reviewed, the CEC may also adjudicate its device-relatedness. Any analysis of the primary and secondary safety endpoints will be based on CEC-adjudicated data.

AEs identified in the subset of patients completing the 12M extended follow-up will not be adjudicated,

Essential Medical, Inc. Protocol
No. PSD-212 Rev.C
as the safety endpoints are through 30 days.

10. Medication

There are no prohibited medications for this clinical investigation.

Only the following medications will be recorded on the CRF: Aspirin, Clopidogrel, Vitamin K Antagonists, and NOAC's (eloxaban, rivaroxaban, dabigatran, apixaban) at baseline through 30-day follow-up, inclusive of medications given in the cath lab.

11. Vulnerable Population

The intended patient population of this post-market registry does not meet the criteria of vulnerable population as defined in ISO 14155, Section 3.44.

12. Outsourcing

The Sponsor may transfer some duties and functions related to the clinical study, such as monitoring, data management, etc. to an external organization (such as a contract research organization or individual contractor). When outsourcing does occur, the ultimate responsibility for the quality and integrity of the clinical study will reside with the Sponsor. All requirements applying to the Sponsor will also apply to the external organization inasmuch as this organization assumes the clinical study related duties and functions of the Sponsor.

13. Data Management

The Sponsor/designee will be responsible for data handling. The Sponsor will be responsible for compiling and submitting all required reports to governmental agencies.

Data will be analyzed by the Sponsor/designee and may be transferred to the Sponsor's locations outside of Europe.

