## 5.4 Safety Endpoint 3: Long-term Device Related SAEs

Objective: To quantify real-world long-term safety using the MANTA device.

Endpoint: The percentage of patients with one or more events on ipsilateral leg with MANTA device as described in the main safety endpoints beyond 30 days for each event:

- VARC-2 major complication
- VARC-2 minor complication (with no major VARC-2 complication)

Subjects to include: All subjects that have enrolled in the longer-term follow-up with a procedure attempt will be included in this analysis.

Statistical analysis (patient based): The number of subjects, percentage of patients and 95% confidence intervals for the percentage of subjects will be calculated at a minimum for subjects experiencing a major VARC2 complication and again for minor VARC2 complication.

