## 5.5 Additional Summaries

Additional summaries will be prepared similar to the effectiveness and safety endpoints using descriptive statistics. These summaries will be prepared for the overall population, by cohort (TAVR vs not TAVR), and by MANTA device size (14 or 18 Fr) at a minimum. Some summaries will be repeated for the 12M subset as appropriate.

At a minimum the following items will be included:

1. Baseline demographics and characteristics
  - Age
  - Gender
  - BMI
  - STS score (TAVR group only)
  - Medical history (prior history of PCI, CABG, Hypertension, LVEF < 20%, kidney dysfunction (GFR < 60 umol/L), pacemaker, peripheral artery disease, stroke/CVA)
  - Medications at baseline

- i. ASCAL
- ii. Oral anticoagulants
- iii. New oral anticoagulants
- iv. Clopidogrel
- v. Heparin
- vi. Other anticoagulants

2. Procedure characteristics

- Target artery characteristics
  - i. Diameter
  - ii. Calcification
  - iii. Side (left/right/both)
  - iv. Presence of scar tissue in groin on treated side
- Procedure type
- Hemostasis time (descriptive statistics and success (<10 min) – primary performance endpoints
- MANTA procedure time
- MANTA device sizes
  - i. Instances of size mismatch (where the device size exceeds the artery size)
  - ii. Sheath-to-femoral-artery ratio
- Device deficiencies
- Procedure success (proportion of subjects with no VARC-2 major complications within 30 days)

3. 30 Day Follow-up / Exit

- Average follow-up (exit date – procedure date) in days
- Medication at each time point (during procedure, post procedure, 30 day follow-up/exit)
- Summarize type of follow-up (in person/at office or via phone call)
- Reason for study exit (as reported via eCRFs).

4. 12 Month Follow-up (for subset of 100-120 subjects)

- Average follow-up (exit day of 12 month – procedure date) in days
- Provide baseline demographics for subjects that had 12M follow-up comparing to overall population.
- Target Femoral Access Site Visual Assessment
- Adverse Events occurring on MANTA side only from day 38 to 12M visit
- Medication at each time point (12month follow-up/exit)
- Reason for study exit (as reported via eCRFs)

5. Analysis of primary and secondary safety endpoints and hemostasis by on and off-label device use. On label means meeting indications per IFU.

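### Protocol 9.7 withholds adjudication by when an event is found, not by its onset, so a complication within 30 days first reported at 12 months can miss every safety endpoint, in conflict with Protocol 9.5.1 and SAP section 3

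*Protocol*

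**What the plan says.** **How the 12M subset arises.** Under Protocol 7.7, subjects leave the study after the 30 ± 7 day follow-up, which the synopsis allows by phone. For the 12M visit, subjects already exited are contacted again and sign a consent addendum. The subset is 100 to 120 of up to 500.

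**What is collected at 12M.** Protocol 8.6: "Only AEs related to the MANTA access site or the ipsilateral leg will be collected at the 12M visit". No earliest onset date is set.

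**How those events are handled.** Protocol 9.7: "AEs identified in the subset of patients completing the 12M extended follow-up will not be adjudicated". The reason given is "as the safety endpoints are through 30 days". Protocol 8.6 adds: "AE data from the 12M visit will be analyzed separately from the primary safety endpoint, as 12M data will only be available on a subset".

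**What feeds the endpoints.** Protocol 9.7 and SAP section 3: "Any analysis of the primary and secondary safety endpoints will be based on CEC-adjudicated data". SAP 5.2 and 5.3 count complications within 30 days of the procedure, and 5.2 leaves the Major classification to the CEC. The long-term endpoint in SAP 5.4 counts events "as described in the main safety endpoints beyond 30 days for each event". SAP 5.6 item 2 summarises long-term MANTA AEs from Day 31. SAP 5.5 item 4 lists "Adverse Events occurring on MANTA side only from day 38 to 12M visit".

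**Text pointing the other way.** Protocol 9.5.1 sends every MANTA-leg AE that the investigator rates possibly, probably or definitely device-related to the CEC, with no 12M exception. SAP section 3 gives the CEC the same remit for device-related AEs and does not repeat the 12M exclusion.

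**The concern.** Protocol 9.7 argues from onset but acts on discovery. That the endpoints stop at 30 days is a good reason not to adjudicate an event that began in month 6. It is no reason to leave out one that began in week 3 and came to light late, because such an event is exactly what the 30-day endpoint is meant to count.

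The situation can occur. A subject whose 30-day contact takes place on Day 23 is exited with a week of the endpoint period still to run, and an earlier event can be missed in a phone contact. If that subject later attends the 12M visit, the event may be recorded there for the first time. Which rule the team then follows decides whether it counts.

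The 30-day complication rates are at stake. SAP section 5 sets their 95% confidence intervals against pre-market and literature rates, in a registry that serves the EU post-market follow-up requirement.

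**Working it through.** The plan states no figure for this point, so there is none to reproduce. The check has three parts.

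**1. Where does an event first reported at 12M go if 9.7 is followed?** Inputs: no adjudication (9.7); adjudicated data only for the 30-day endpoints (9.7, SAP section 3); start days from SAP 5.4, 5.6 item 2 and 5.5 item 4.

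| Onset day | SAP 5.2 / 5.3 | SAP 5.4 | SAP 5.6 item 2 | SAP 5.5 item 4 |
|---|---|---|---|---|
| 10, 25, 30 | no (not adjudicated) | no | no | no |
| 31, 35 | no (onset too late) | yes | yes | no |
| 38, 200 | no (onset too late) | yes | yes | yes |

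Only the first row is a gap: those events reach no endpoint and neither of the 12M summaries. They remain eligible for the general AE tables and listings in SAP 5.6, which cover all events during or after the procedure. If 9.5.1 and SAP section 3 are followed instead, a device-related event in the first row goes to the CEC and can count in 5.2 or 5.3.

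The earliest 30-day visit is Day 30 − 7 = 23, leaving Days 24 to 30, which is 7/30 = 23% of the endpoint period, after exit.

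**2. Size.** Assume N = 500, the planned maximum.
- Share of subjects in the subset: 100/500 = 20% to 120/500 = 24%.
- Each omitted event lowers a rate by at most 1/500 = 0.2 points. It is less if the subject already counts, because the endpoints are patient-based.
- Illustrative base: 4.2% Major VARC-2 (FDA PMA row, SAP Table 2) × 500 = 21 events; 1/21 = 4.8% of that count.
- The documents give no number of such events. Assumed range: 0 to 3.

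| Late events restored | Major rate | Exact 95% CI |
|---|---|---|
| 0 | 21/500 = 4.2% | 2.62 to 6.35 |
| 1 | 22/500 = 4.4% | 2.78 to 6.59 |
| 2 | 23/500 = 4.6% | 2.94 to 6.82 |
| 3 | 24/500 = 4.8% | 3.10 to 7.06 |

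Three is generous. At 4.2%, the whole subset would have 0.042 × 100 = 4.2 to 0.042 × 120 = 5.0 Major events, so three would be 60% to 71% of them, all unknown to the site until 12M.

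Direction: the omission can only lower the Major rate. It lowers the Minor rate too, with one exception. SAP 5.3 counts Minor only in subjects without a Major event, so a subject already counted as Minor whose late-reported Major is dropped stays in the Minor count.

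**3. Would sorting by recorded onset be enough?** No. SAP section 6 replaces a missing onset month with the procedure date and a missing day with the first of the month (or the procedure date if that is later). Take a procedure on 10 March and an event on 25 April, Day 46, recalled as April only. It is dated 1 April, Day 22. Sorting on that date would move a late event into the 30-day endpoint.

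**The case against.** **The plan may already handle this.** Protocol 9.5.1 and SAP section 3 route device-related AEs to the CEC without a 12M exception, SAP 5.2 and 5.3 set no condition on the visit at which an event is found, and the reason in 9.7 suggests that only later events were meant. This stands in part. A reader might infer that the plan definitively excludes these events from every endpoint, and the documents do not support that. But 9.7 is the specific rule for the subset, and 9.7 and SAP section 3 describe adjudication as running in parallel with enrollment, which had closed when the SAP was drafted. The result is a conflict, not a resolution in either direction.

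**Keeping the second look separate is deliberate.** Protocol 8.6 gives a reason: only a subset has 12M data. That subset is selected, starting from the highest-enrolling sites and requiring new consent, so counting its late-reported events makes 30-day ascertainment unequal. It would also disturb the planned 8.6 comparison of patients with and without 12M follow-up on 30-day outcomes. This stands and shapes the fix.

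**Early exit is a wider gap.** An event after a Day 23 exit goes unseen in any subject, and the 12M visit can recover it only in the subset. True, but it does not justify setting aside an event once it is known.

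**Nothing disappears.** A reader might infer that the event goes unreported. It does not: besides SAP 5.6, Protocol 9.5.1 puts device-related events through complaint and vigilance review. What is lost is its place in the endpoint rates.

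**Conclusion.** The point holds as a conflict between passages and as a rule that does not match its own reason. If 9.7 is followed as written, a MANTA-leg event with onset by Day 30 first reported at 12M is left out of the 30-day endpoints and of SAP 5.4. If 9.5.1 and SAP section 3 are followed, a device-related event of this kind can count. The plan does not say which prevails.

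The effect is probably very small: at most 0.2 points per event at an assumed N of 500, and 0 to 0.6 points over the assumed range of 0 to 3 events, with the true number likely near zero. A reader might infer that known complications have been lost or that the published rate is materially biased. The documents show no such event, and the illustrative shifts lie well inside the confidence interval. The point merits correction because the omission can only lower the primary safety rate and costs little to remove.

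**What to change.** - **Protocol 9.7 and 8.6, SAP section 3:** limit the no-adjudication rule to events with onset after the 30-day endpoint window. State the last day of that window, since Protocol sections 5 and 8.3.1 say 30 ± 7 days and SAP 5.2 and 5.3 say 30 days.
- **Late-reported events:** send any MANTA-leg AE that meets the relatedness criteria in 9.5.1 and has a documented, not imputed, onset within the window to the CEC, whenever it is reported. If it is adjudicated Major or Minor, count it in SAP 5.2 or 5.3.
- **Reporting:** flag these events and give the 30-day rates with and without them.
- **8.6 comparison:** leave them out of the comparison of 12M with non-12M patients, so that both groups are judged on the same follow-up.
- **Timing:** Protocol 6.5.6 places endpoint analysis (October 2019) before study close (September 2020), so say that the final report updates the 30-day counts after the 12M visits.

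Cost: a few sentences across the two documents, an extra row in the 30-day tables and a few CEC reviews at most. The downside is slightly fuller ascertainment in the 12M subset, which the with-and-without rates make visible.

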Appendix 1. Instructions for Use

## 1 Purpose

This Statistical Analysis Plan (SAP) is intended to provide additional details for planned summaries of the data in support of generating a final report for the clinical study, "Post-Market Clinical Registry to Evaluate the Safety and Performance of MANTA Vascular Closure Device Under Real World Conditions in European Union (MARVEL)", protocol ID PSD-212 Rev C.

All analyses will be performed using validated statistical software such as SAS version 9.4 or other well-known statistical packages.

Note that a tables/figures/listings (TFL) template was prepared in support of this SAP to help clarify expected summaries.

## 2 Background

The MARVEL trial is an observational post-market study intended to gather real world outcome data on the use of the CE marked MANTA Vascular Closure Device following percutaneous cardiac or peripheral procedures using large bore (10-18F ID) interventional devices. This study also fulfills EU regulatory requirements for post-market clinical follow-up.

The 14F MANTA Vascular Closure Device is indicated for closure of femoral arterial access sites following the use of 10-14F devices or sheaths (maximum OD/profile of 18F), and the 18F MANTA Vascular Closure Device is indicated for closure of femoral arterial access sites following the use of 15-18F devices or sheaths (maximum OD/profile of 25F). Procedures include transfemoral TAVI, EVAR and TEVAR; however, all participants must meet indications for use and contra-indications as described in the Instructions for Use and sites must adhere to registry requirements.

Up to 500 patients will be implanted at up to 20 sites with MANTA VCD which will consist of 2 cohorts.

- Cohort 1 restricted to TAVI procedures (T Group) - T Group will require a CT scan at baseline and a femoral angiogram post-MANTA deployment.
- Cohort 2 includes all other on-label CE-marked medical devices in accordance with MANTA device IFU excluding TAVI procedures (NT Group) - such as mechanical circulatory support (MCS), EVAR and TEVAR procedures. NT Group does not require CT scan at baseline or angiography post-MANTA deployment.

The original protocol specified that subjects would be followed-up at 30-days post-procedure. Mid-study, the protocol was updated to extend follow-up by adding a 12M visit for a subset of 100-120 subjects.

The data collection schedule is provided in Table 1 below.

**Table 1.** Data collection schedule

Assessment/ Interval	Screening	Index Procedure	MANTA Procedure			Post procedu re	Hospital Discharge	Follow-up	
			pre- MANTA closure	MANTA closure	post- MANTA closure			30D (±7 days)	12M  (± 30 Days)
Subject Eligibility/ Informed Consent	X								
Medical History	X								
Medication	X 	X 	X 	X 	X 	X 	X 	X 	X 
CT Angiographic Scan	X 2*								
ACT/Systolic Blood Pressure				X 					
Femoral Angiography		X			X 4*				
Target Femoral Access Site Visual Assessment					X	X	X	X	X
Time to Hemostasis					X				
Time to Ambulation							X		
Adverse Events		X	X	X	X	X	X	X	X

1. Medications (only Aspirin, Clopidogrel, Vitamin K Antagonists and, NOAC's: [eloxaban, rivaroxaban, dabigatran, apixaban] will be collected)
2. Screening Visit CT Scan to assess both limbs for presence/absence of calcium, atherosclerotic disease, tortuosity, and acceptable flow rates.
3. Prior to MANTA closure, record ACT and systolic BP (per contraindications BP<180; recommend ACT below 250 seconds prior to closure)
  - \* #2 CT Angiographic Scan and #4 Post MANTA femoral angiogram are required in cohort 1
4. Post-MANTA closure, perform target (ipsilateral) common femoral angiography from contralateral access site to ensure patency into the ipsilateral common femoral artery
5. A subset of study enrollment, 100-120 subjects at up to 7 sites, will complete the 12M follow-up visit.

### 3 Clinical Events Committee

An independent Clinical Events Committee (CEC) will be established for this study. The CEC will include members qualified to review adverse event data for this study. During the CEC review, a designated CEC member is responsible for reviewing the documentation for events that occurred in their country. If complex events emerge, the designated CEC member can ask the CEC Chair to convene a conference call to discuss the specific event(s). The CEC will be established and operate according to a charter defined prior to the initiation of the trial. The CEC will review individual adverse events that meet the following criteria:

- AEs that are considered by the investigator to be definitely, probably or possibly device related will be adjudicated by CEC parallel to enrollment. Additionally, outcomes not associated with the MANTA device may also be adjudicated by CEC.

The primary responsibilities of the CEC over the course of the study are to review and refine serious adverse event definitions, and to review and adjudicate serious adverse events.

The CEC will determine if each reviewed adverse event meets the definition of a VARC-2 Major femoral vascular complication or a VARC-2 Minor femoral vascular complication or neither definition. For each AE reviewed, the CEC may also adjudicate its device-relatedness. Any analysis of the primary and secondary safety endpoints will be based on CEC-adjudicated data.

Specifically, the CEC will review:

- Any adverse events that are possibly, probably or definitely related to the MANTA device. The CEC members will adjudicate whether each event is a VARC-2 Major or Minor Femoral Vascular Complications within 30 days following procedure or whether it is no-event (does not meet either definition). determine the percentage of subjects with one or more VARC-2 Major or Minor Femoral Vascular Complications within 30 days following procedure.

The following events below will not be submitted for adjudication as these events do not meet the definitions of VARC-2 Major/Minor vascular complications or definitions in the MARVEL Protocol PSD-212.

- Hematoma: less than 2 cm in size or no size is recorded for the hematoma and it requires no treatment or requires only prolonged/adjunctive compression.
  - Rationale: Per MARVEL Protocol PSD-212, a hematoma is defined as an expanding or non-expanding subcutaneous mass of blood greater than 2 cm in its longest axis, confirmed by ultrasound, and VARC-2 excludes percutaneous closure device failure requiring only manual compression from minor vascular complications.
- Minor Bleeding: requiring no treatment or requiring only prolonged/adjunctive compression.
  - Rationale: Per VACR-2 criteria, minor bleeding requiring adjunctive compression is not categorized as a VARC-2 major/minor vascular complication and percutaneous closure device failure requiring only manual compression is excluded from minor vascular complications.

The CEC member will provide the following assignments for each AE:

- If AE resulted in death, classify death:

- Cardiac
    - Non-cardiovascular
    - Vascular
  - If AE resulted in bleeding complications: (yes/no)
    - If yes, define event type below:
      - BARC 0
      - BARC 1
      - BARC 2
      - BARC 3a
      - BARC 3b
      - BARC 3c
      - BARC 4
      - BARC 5a
      - BARC 5b
  - VARC-2 Major Complication (yes/no)
    - Type of classification (from drop down list)
  - VARC-2 Minor Complication (yes/no)
    - Type of classification (from drop down list)
  - Device relatedness
    - Not related
    - Unknown
    - Possible
    - Probably
    - Definite
  - Procedure relatedness
    - Not related
    - Unknown
    - Possible
    - Probably
    - Definite

The CEC adjudications will be documented in a controlled limited access Excel spreadsheet.

